**Table 4: Investigational Product**

	Investigational Product
Product Name	AVXS-101
Unit Dose	$6.0 \times 10^{13}$ vg (Dose A) $1.2 \times 10^{14}$ vg (Dose B) $2.4 \times 10^{14}$ vg (Dose C)
Route of Administration	Intrathecal Injection
Physical Description	Once thawed, AVXS-101 is a clear to slightly opaque, colorless to faint white solution, free of visible particulates

### 9.2. Prior and Concomitant Medications

Prior and concomitant medications will be captured in the electronic Case Report Form (eCRF) from two weeks prior to study dosing until the End of Study visit.

#### 9.2.1. Prophylactic Administration of Prednisolone

An antigen specific T-cell response to the AAV vector was observed in the ongoing Phase 1 clinical study investigating AVXS-101 treatment via IV infusion. This is an expected response between 2-4 weeks following gene transfer. One possible consequence to such antigen specific T-cell response is clearance of the transduced cells and loss of transgene expression.

In an attempt to dampen the host immune response to the AAV based therapy, patients will receive prophylactic prednisolone (glucocorticoid) (approximately 1 mg/kg/day) 24 hours prior to AVXS-101 dosing. Treatment will continue for approximately 30 days in accord with the following treatment guideline:

- Until at least 30 days post-injection: 1 mg/kg/day
- Weeks 5 and 6 post-injection: 0.5 mg/kg/day
- Weeks 7 and 8 post-injection: 0.25 mg/kg/day
- Week 9 post-injection prednisolone discontinued

Liver function testing should guide each step of the taper, and liver function tests should be checked prior to prednisolone discontinuation. If the GGT, AST or ALT values are  $\geq 2 \times$  ULN, then the present dose of prednisolone will be adjusted as needed until the GGT, AST, and ALT values decrease below threshold, at which point the taper may continue. Liver function tests

should also be checked approximately 2 weeks after the taper has concluded and prednisolone has been discontinued to evaluate for rebound elevation of GGT, AST or ALT levels. Variance from these recommendations will be at the discretion of the Investigator based on potential safety issues for each patient. If another glucocorticoid is used in place of prednisolone by the Investigator, similar considerations should be taken into account after 30 days and tapered as appropriate and at the discretion of the Investigator.

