**Investigational product, dosage and mode of administration:**

This is an open-label dose comparison study involving up to three AVXS-101 dosing cohorts of three patients each.

The AVXS-101 dosing cohorts are as follows:

- Cohort 1 (n=3) AVXS-101 6.0 × 10^13 vg (Dose A)
- Cohort 2 (n=3) AVXS-101 1.2 × 10^14 vg (Dose B)
- Cohort 3 (optional) (n=3) AVXS-101 2.4 × 10^14 vg (Dose C)

AVXS-101 will be delivered to the IT injection procedure location premixed with 1.5 mL of an appropriate [REDACTED] approved and labeled for pediatric use for radiographic monitoring of the injection via lumbar IT injection. The total volume of AVXS-101 [REDACTED] will NOT exceed 8 mL. Sedation/anesthesia is required for all patients receiving AVXS-101. Method and medications will be at the discretion of the local anesthesiologist but should incorporate a sufficient degree of sedation or anxiolysis to ensure analgesia and lack of movement for the procedure and post-procedure Trendelenburg positioning placement (tilted head-down at 30° for 15 minutes). Patients will be placed in the Trendelenburg position, at 30°, for 15 minutes following administration of the AVXS-101 vector to enhance distribution to cervical and brain regions.

In an attempt to dampen the host immune response to the adeno-associated virus (AAV) derived therapy, patients will receive prophylactic prednisolone (glucocorticoid) (approximately 1 mg/kg/day) 24 hours prior to AVXS-101 dosing. Treatment will continue for approximately 30 days in accordance with specified guidelines for tapering.

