Blood for diagnostic confirmation testing	X													To be performed by central laboratory.

Study Interval	Baseline Screening	Vector (AVXS-101) Injection (Inpatient)			Follow-up (Outpatient)									Notes	
		-1	1	2-3	7	14	21	30	44	60	72	Monthly Through M12 	M15/ EOS		
Study Day	-60 to -2				± 2							± 7			
Window															
Saliva, Urine, and Stool Samples (for viral shedding)		X		(X)	(X)	(X)		(X)						(X): Sites participating in the viral shedding sub-study will collect 24-hour full volume samples for urine and feces through 24 and 48 hours. All other sites will collect singular urine and feces samples within 24 hours and 48 hours of dosing. Full urine and feces samples will be collected for patients ≥ 48 months who are no longer in diapers.	
Baseline Screening of Biological Mother (Anti-AAV9 Ab)	(X)													Serum sample collected at screening for anti-AAV9 antibodies. (X): Baseline procedure must be completed within 30 days of dosing.	
Immunology Labs (Anti-AAV9/SMN)	(X)				X	X	X	(X)						(X)*: Additional sampling may be performed at subsequent time points if ELISpot value(s) continue to be elevated, based on further discussion with the PI and Medical Monitor.	
Immunology Labs (IFN-γ T-cells)					X	X	X	(X)						(X): Additional sampling may be performed at subsequent time points if ELISpot value(s) continue to be elevated, based on further discussion with the PI and Medical Monitor.	
Prophylactic Prednisolone		X	X	X	X	X	X	X	X	X	X			See Section 9.2.1. Daily dosing from 24 hours prior to scheduled AVXS-101 dose and continued as per protocol.	
Study Product Administration			X												
Photograph Injection Site			X		X	X	X	X							
Adverse Events	X	X	X	X	X	X	X	X	X	X	X	X	X		

Study Interval	Baseline Screening	Vector (AVXS-101) Injection (Inpatient)			Follow-up (Outpatient)									Notes
		-1	1	2-3	7	14	21	30	44	60	72	Monthly Through M12 	M15/ EOS	
Study Day	-60 to -2													
Window					$\pm$ 2							$\pm$ 7		
Prior and Concomitant Medications	To be collected from 2 weeks before study dosing until final study visit													

AE = adverse event; ALT = alanine aminotransferase; AST = aspartate aminotransferase; CK-MB = Creatinine kinase-MB (isozyme MB);  
ECG = electrocardiogram; ELISpot = enzyme-linked ImmunoSpot; GGT = gamma glutamyl transferase; IFN- $\gamma$  = interferon gamma; PI = Principal Investigator; SoA = Schedule of Assessments;

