### 7.4.2. Specific Medication Subgroup

The total number of days receiving prednisolone and total cumulative dose of prednisolone administered during the entire study (mg/kg) will be computed for each patient. Only the data recorded on the prednisolone dosing log will be used in this derivation.

To compute total cumulative dose, the total dosing period is subdivided into dosing intervals represented by constant dose levels. On the day of a dosage change, the entire day is represented under the new dosing interval at the new dose.

For example, consider a patient who receives 1.0 mg/kg of prednisolone for Day 1 to Day 30, then on Day 31, dose is lowered to 0.5 mg/kg until Day 42. On Day 43, the dose is lowered to 0.25 mg/kg and continues until Day 56 when prednisolone dosing stops. For this patient,

$$\begin{aligned}\text{Total cumulative dose} = & (1.0 \text{ mg/kg} \times 30 \text{ days}) + \\ & (0.5 \text{ mg/kg} \times 12 \text{ days}) + \\ & (0.25 \text{ mg/kg} \times 14 \text{ days}) = 39.5 \text{ mg/kg}\end{aligned}$$

Exposure will be summarized overall and by actual dose received and age group for the SS.

A listing of AEs will be produced for patients who did not follow the protocol-defined taper, defined as those patients with less than 56 days of total time of prednisolone dosing.

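### For two of the three prednisolone taper steps, the liver test meant to guide the step is scheduled on or just after it, and the documents disagree on the length of the course

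*Protocol*

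**What the plan says.** Protocol Section 9.2.1 sets the principle: "Liver function testing should guide each step of the taper, and liver function tests should be checked prior to prednisolone discontinuation". If GGT, AST or ALT is at least twice the upper limit of normal, the current dose is adjusted and the taper resumes once values have fallen. A further check is due about two weeks after prednisolone has been stopped.

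The same section gives the course in four lines:

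- The starting level is given as "Until at least 30 days post-injection: 1 mg/kg/day".
- The first reduction follows, as "Weeks 5 and 6 post-injection: 0.5 mg/kg/day".
- The second reduction is given as "Weeks 7 and 8 post-injection: 0.25 mg/kg/day".
- The end of the course is given as "Week 9 post-injection prednisolone discontinued".

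Other places describe the same course:

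- **Protocol synopsis:** "Treatment will continue for approximately 30 days in accordance with specified guidelines for tapering". The lead-in sentence of Section 9.2.1 gives the same duration.
- **Schedule of Assessments (Protocol Table 3, repeated in SAP Section 19.2):** the prednisolone row is marked at every column from Day -1 through Day 72. Its note refers to Section 9.2.1 and adds "Daily dosing from 24 hours prior to scheduled AVXS-101 dose and continued as per protocol".
- **SAP Section 7.4.2:** a worked example lowers the dose on Day 31, then "On Day 43, the dose is lowered to 0.25 mg/kg and continues until Day 56 when prednisolone dosing stops". Patients with fewer than 56 days of dosing count as not having followed the taper.

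Around the taper, liver tests are scheduled on Days 30, 44, 60 and 72, then monthly from Month 3 (Protocol Tables 3 and 7). SAP Section 3.5 limits the Day 44 and Day 72 visits to Cohort 3 patients enrolled after Amendment 7 took effect.

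**The concern.** A test can guide a step only if its result is known before the step is taken. The weeks in Section 9.2.1 and the visit days in the Schedule of Assessments appear to have been set separately, and they do not interlock at the second reduction or at discontinuation. A site that follows both literally reduces the dose, and may stop it, before the matching visit takes place.

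Appendix 3 of the protocol says that Amendment 7 added liver monitoring visits after a case of acute liver failure elsewhere in the programme, and that the taper text was rewritten for the same reason. The calendar should therefore deliver the safeguard that the text describes.

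The differing descriptions of the course also affect two later items: the date of the rebound check, and the SAP's identification of patients who departed from the taper.

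**Working it through.** **Inputs.** Injection is study day 1 (SAP Section 6.2.2). Steps come from Protocol Section 9.2.1 and SAP Section 7.4.2, and test days from Protocol Tables 3 and 7. Month 3 is taken as Day 90 (SAP Section 6.5).

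**The plan's own figure.** The SAP example reproduces: 1.0 × 30 + 0.5 × 12 + 0.25 × 14 = 30 + 6 + 3.5 = 39.5 mg/kg, over 30 + 12 + 14 = 56 days. It fixes the SAP's steps at Days 31 and 43 and counts Day 56 as the last dosed day.

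**Week to study day.** Week k starts on Day 7(k − 1) + 1 if the injection day opens Week 1 (count A), or one day later if Week 1 opens the day after (count B).

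| Step | Count A | Count B | Test | Test day minus step day |
|---|---|---|---|---|
| First reduction, as Week 5 | Day 29 | Day 30 | Day 30 | +1 / 0 |
| First reduction, after 30 full days (SAP example) | Day 31 | – | Day 30 | −1 |
| Second reduction, Week 7 | Day 43 | Day 44 | Day 44 | +1 / 0 |
| First day of Week 9 | Day 57 | Day 58 | Day 60 | +3 / +2 |

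A negative value means that the test comes first. Only the first reduction has one, and only when it is taken on Day 31.

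**Gap before stopping.** Under count A the last stated dose is on Day 56. The latest scheduled test before it is Day 44, and 56 − 44 = 12 days. Week 9 is Days 57–63. Day 60 precedes a stop on Days 61–63, but no dose is stated for any day after Day 56.

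**Visit windows.** The table as extracted does not show clearly which columns carry ±2 and which ±7 days, so both were tried.

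- ±2 days: the Day 44 visit spans Days 42–46 and can precede Day 43. The Day 60 visit spans Days 58–62 and cannot precede Day 57.
- ±7 days: the visits span Days 37–51 and Days 53–67, so either can precede its step.

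The windows permit the right order but do not secure it.

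**Result availability.** Protocol Section 12.14 sends samples to a central laboratory, and Section 12.14.2 has investigators receive results from there. No turnaround is stated. Any turnaround longer than zero widens the gaps above, and by how much cannot be computed.

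**Overlap at the first step.** Under count A, Days 29 and 30 belong both to the 1 mg/kg period and to Week 5 at 0.5 mg/kg. Count B shifts the overlap without removing it.

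**Rebound check, by end of dosing.**

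| Prednisolone ends | Next relevant test | Interval |
|---|---|---|
| Day 57 or 58 | Day 72 | 15 or 14 days |
| Day 63 | Day 72 | 9 days |
| Day 72 (last mark in the row) | Month 3, Day 90 | 18 days |

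**SAP adherence threshold.** Section 9.2.1 starts prednisolone 24 hours before injection. Day -1 plus Days 1–56 is 57 days, whereas the SAP example counts from Day 1 and reaches 56. If the dosing log includes Day -1, a patient who stops after Day 55 has 1 + 55 = 56 days and is not listed. A course running to Day 72 has 1 + 72 = 73 days and is not listed either.

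**The case against.** Section 9.2.1 is advisory. It says what should happen, presents the weeks as a guideline, makes continuation of the taper depend on the results, and leaves variance to the investigator. Nothing forces a site to reduce on Day 43 when a test is due the next day. Section 12.14 allows local samples when an immediate result is needed. Discontinuation is assigned to a week that contains the Day 60 visit, and even a Day 57 stop has the Day 44 test behind it. The SAP example is hypothetical and agrees with the end of Week 8. Reach is small: the Day 44 and 72 visits concern only later Cohort 3 patients, and SAP Section 2.2.1 reports four patients treated in that cohort when the study was terminated.

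Most of this stands and limits the severity. It does not remove the mismatch. Discretion and local sampling are open to a site that notices the problem, but neither is tied to a taper step, and the default calendar still puts the test on or after two of the three steps.

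A reader might infer more than the documents support in three respects:

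- **That every step precedes its test.** It does not, because Day 30 comes before a Day 31 first reduction.
- **That the rebound check is lost.** Day 72 fits a Day 57 or 58 stop well. It fails only if dosing runs to the Day 72 mark, and the note on that row defers to Section 9.2.1, so the mark is weak evidence of a prescribed last dose.
- **That the synopsis sets a 30-day stop.** The same sentence refers to tapering. The figure describes the course poorly, but it is not a rival end date.

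**Conclusion.** The point holds, at moderate severity. The second reduction falls 0–1 day before its test. The start of Week 9 falls 2–3 days before its test, which leaves 12 days between the last earlier scheduled test and the last stated dose when that dose is on Day 56. These are nominal gaps. They assume that the stated weeks are followed and that visits occur on their nominal days.

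Three inconsistencies do not depend on visit windows: the overlap of the first two dose levels around Days 29–30, a stated duration of about 30 days for a course of about eight weeks, and prednisolone marks at Days 60 and 72 against an end at Day 56 or Week 9.

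No efficacy endpoint, test or estimate is affected. The only analysis touched is the SAP listing of adverse events in patients who did not follow the taper. The documents do not show which schedule was intended, and no view is taken here.

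**What to change.** - Reconcile the synopsis, Protocol Section 9.2.1, the prednisolone row in Protocol Table 3 and SAP Section 19.2, and SAP Section 7.4.2. State each taper step and the discontinuation in study days.
- Tie each step to a named existing liver-test visit, or to a local test as Section 12.14 permits, whose result is available beforehand.
- Make the prednisolone marks at Days 60 and 72 agree with the reconciled end of dosing, or explain them. Confirm that the Day 72 visit still falls about two weeks after it.
- Restate the SAP's taper-departure definition to match. Say whether the Day -1 dose counts, and how courses longer than planned are handled.

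The sponsor's clinicians decide which days and doses apply.

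The cost is a protocol clarification and about one SAP sentence. The visits already exist, so no new visit type is needed. Because the study was closed early, the practical gain may lie mainly in the SAP definition and in how the study report describes the taper.

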### **9.2.2. Prohibited Medications**

Concomitant use of any of the following medications is prohibited:

- Drugs for treatment of myopathy or neuropathy
- Agents used to treat diabetes mellitus
- Therapy received with the intent to treat SMA (e.g., valproic acid, nusinersen).
  - Oral beta-agonists must be discontinued at least 30 days prior to gene therapy dosing.
  - Inhaled beta agonists may be used to treat respiratory complications of SMA provided such medications are dosed at clinically appropriate levels
- Ongoing immunosuppressive therapy, plasmapheresis, immunomodulators such as adalimumab, or immunosuppressive therapy within 3 months of starting the trial (e.g., corticosteroids, cyclosporine, tacrolimus, methotrexate, cyclophosphamide, IV immunoglobulin, rituximab)

Corticosteroid usage following completion of the prednisolone taper is permissible at the discretion of the managing physician as part of routine clinical management. The use of prednisone in such circumstances should be documented appropriately as a concomitant medication, and the event precipitating its usage should be appropriately documented as an AE.

Should the use of corticosteroids (aside from inhaled corticosteroids for bronchospasm) be considered as part of care during the course of the prednisolone taper, this medical management should be discussed with the AveXis medical monitor, who will be responsible for any indicated medication adjustments related to the taper.

### **9.2.3. Vaccinations**

Where feasible, the vaccination schedule should be adjusted appropriately to accommodate prednisolone use. When avoiding vaccination while on steroids represents an undue delay or interruption of a vaccination schedule, vaccination should continue at the discretion and judgment of the treating physician given 1) the importance of maintaining childhood vaccination in this population and 2) the published literature that indicates that vaccination while on steroid doses 1 mg/kg/day or below is safe and effective ([Mendell 2017](#); [Kroger 2018](#)).

## **9.3. Treatment Compliance**

AVXS-101 will be administered as a one-time IT injection.

### **9.4. Randomization and Blinding**

This is an open-label study. See [Section 10.7](#) for a description of the dosing cohorts.

## 10. STUDY PRODUCT MATERIALS AND MANAGEMENT

AVXS-101 was manufactured in accordance with current Good Manufacturing Practice (cGMP).

### 10.1. Study Product

AVXS-101

### 10.2. Study Product Dose and Dose Justification

Patients will receive a one-time dose of AVXS-101  $6.0 \times 10^{13}$  vg,  $1.2 \times 10^{14}$  vg or a third dose of  $2.4 \times 10^{14}$  vg, if determined necessary via IT injection. The delivery directly into the CSF via IT injection allows for reduction of the amount of viral vector approximately by a factor of 10 with equal distribution and efficacy throughout the CNS, reducing viral vector loads and further optimizing safety (see [Section 5.2](#) for additional details). Selection of the appropriate dose and justification for studying all dose escalations are further supported by ongoing safety and efficacy reviews of clinical findings from the patients receiving previous doses as described (see [Section 7.1](#)). The highest selected dose will be  $2.4 \times 10^{14}$  vg delivered IT. Doses up to  $1.1 \times 10^{14}$  vg/kg have been safely administered systemically (IV) to children weighing up to 8.4 kg (total dose  $9.24 \times 10^{14}$  vg). In addition, in preclinical studies, the IT administration of sCAAV9.CB.SMN was safe and well tolerated up to 14 months post injection in large non-human primates at a dose of  $2 \times 10^{13}$  vg/kg ([AVXS-101 Investigator's Brochure](#)).

### 10.3. Study Product Packaging and Labeling

AVXS-101 kits are labeled with a specific kit number and batch/lot number assigned at the cGMP facility. The content of the labeling is in accordance with the local regulatory specifications and requirements.

### 10.4. Study Product Storage and Destruction

AVXS-101 kits will be stored in an appropriate, locked room under the responsibility of the Investigator or other authorized persons (e.g., pharmacists) in accordance with local regulations, policies, and procedures. Control of storage conditions, especially control of temperature (e.g., refrigerated/freezer storage) and information on in-use stability and instructions for handling prepared AVXS-101 should be managed in accordance with the Pharmacy Manual.

The vessel used for delivery of the vector should be resealed and processed for destruction in accord with applicable biohazardous waste guidelines for disposal.

### 10.5. Study Product Preparation

Preparation of AVXS-101 will be done aseptically under sterile conditions by a pharmacist.

AVXS-101 will be pre-mixed with an appropriate [REDACTED] approved and labeled for pediatric use for radiographic monitoring of the injection via lumbar IT injection. The total volume of AVXS-101 [REDACTED] will NOT exceed 8 mL, as outlined in the Pharmacy Manual.

The dose-delivery vessel will be delivered to the designated pediatric intensive care unit (PICU) patient room or other appropriate setting (e.g., interventional suite, operating room, dedicated

procedure room) with immediate access to acute critical care management. The vessel will be delivered in accord with the Pharmacy Manual.

## 10.6. Study Product Administration

Patients will receive AVXS-101 IT injection under sterile conditions in a PICU patient room or other appropriate setting (e.g., interventional suite, operating room, dedicated procedure room) with immediate access to acute critical care management. After patients are admitted, vitals will be monitored immediately after dosing and every 15 ( $\pm$  5) minutes for four hours and every hour ( $\pm$  15 minutes) for 24 hours following the AVXS-101 dosing procedure.

Sites are instructed to use an atraumatic needle inserted with the bevel parallel to the dura fibers; this has been shown to considerably reduce damage to the dura and consequently decrease the risk for CSF leak after lumbar puncture including in children ([Kiechl-Kohlendorfer 2003](#); [Ebinger 2004](#)).

Sedation/anesthesia is required for all patients receiving AVXS-101. Method and medications will be at the discretion of the local anesthesiologist but should incorporate a sufficient degree of sedation or anxiolysis to ensure analgesia and lack of movement for the procedure and post-procedure Trendelenburg positioning placement. Patients will be placed in the Trendelenburg position, tilted head-down at 30° for 15 minutes following administration of vector to enhance distribution to cervical and brain regions.

AVXS-101 will be administered by an Investigator [REDACTED]

[REDACTED] Patients will be placed in the lateral decubitus position and a catheter with stylet will be inserted by a lumbar puncture into the L3-L4 or L4-L5 interspinous space into the subarachnoid space. Subarachnoid cannulation will be confirmed with the flow of clear CSF from the catheter. Approximately 4 mL CSF will be removed for Dose A and Dose B, a volume of CSF closely approximating the volume of AVXS-101 plus contrast injected (up to 7 mL) will be removed for Dose C and disposed of as per institutional guidelines. AVXS-101 in the pre-mixed contrast solution will be injected directly into the subarachnoid space. Flushing of the injection needles with 0.5 mL saline will be allowed as per institutional standards/guidelines.

